## 5.3.14. Work Limitations Questionnaire (WLQ)

#### 5.3.14.1. Definition

The objective of the WLQ is to assess the on-the-job impact of chronic health problems and/or treatment ("work limitations") in adults. It is a PRO tool, consisting of 8 items in the short form version. The subject's impressions are captured using 5-point Likert scales. The recall period is 2 weeks.

#### **Step 1: Assign Numerical Values to Each Response**

There are 4 scales within the WLQ-Short Form, each consisting of 2 items, and each of the 8 items is given a score as follows:

Scale/Items	Coding
WLQ Time Management	
"Get going easily at the beginning of the	5=difficult all of the time
workday"	4=difficult most of the time
5	3=difficult some of the time
"Start on your job as soon as you arrived at	2=difficult a slight bit of the time
work"	1=difficult none of the time
, one	[set to missing value]=does not apply to my
	job
WLQ Physical Tasks	
"Sit, stand, or stay in one position for longer	1= able all of the time
than 15 minutes while working"	2= able most of the time
C C	3= able some of the time
"Repeat the same motions over and over again	4=able a slight bit of the time
	5=able none of the time

while working"	[set to missing value]=does not apply to my job
WLQ Mental-Interpersonal Tasks	
"Concentrate on your work"	5=difficult all of the time 4=difficult most of the time
"Speak with people in-person, in meetings or	3=difficult some of the time
one the phone"	2=difficult a slight bit of the time
	1=difficult none of the time
	[set to missing value]=does not apply to my
	job
WLQ Output Tasks	
"Handle the workload"	5=difficult all of the time
	4=difficult most of the time
"Finish work on time"	3=difficult some of the time
	2=difficult a slight bit of the time
	1=difficult none of the time
	[set to missing value]=does not apply to my
	job

#### Step 2: Score the Four WLQ Scales

After each of the 8 items is scored, the scores for the 4 WLQ scales are determined. For each the of 4 WLQ scales, the following 2 steps will be performed:

- (i) Compute the average item score for a scale, including addressing missing data.
- (ii) Convert the average item score to a 0-100 range.

#### Average Item Score

The average item score within a scale is calculated by summing the non-missing item scores within a scale and then dividing by the number of items with non-missing answers within the scale (i.e., not including items coded as missing). For example, if a respondent answers items in the Time Management scale as follows:

"Get going easily at the beginning of the workday" = 2

"Start on your job as soon as you arrived at work" = 4

First, sum the item scores: 2+4. Then divide by the number of items with valid answers, i.e., divide by 2. Your answer is therefore 6/2=3.0.

A scale score can still be calculated even if one of the responses within a scale is missing (either left blank or a "does not apply to my job" response). The scale score is calculated based on the

one non-missing item's score. In this case, the average item score is the value of the non-missing item score.

If both of the items within a scale are missing, the scale cannot be scored and the scale score will be treated as missing data.

#### Converting the Average Item Score to the Scale Score

To obtain the final WLQ Scale Score, convert average item score to a 0-100 range using the following formula:

WLQ Scale Score = 25\*(average item score-1)

For example, using the average item score from above, the WLQ Time Management Scale Score is: 25\*(3-1) = 50.

#### Step 3: Checking and Fixing Physical Scale Score Errors

Although the response categories in the Physical Scale are different than the other 3 scales, some people may not notice the change in wording. They report on the amount of time they had difficulty while they should be reporting on the amount of time they did not have difficulty.

If the answers to the Physical Scale items contradict the answers in the other 3 scales, it can be reasonably inferred that the respondent didn't notice the direction change.

For these cases, implement the Physical Scale score correction as follows.

If the Physical Scale score computed above is greater than or equal to 75 and the other three scale scores are less than or equal to 30, the Physical Scale needs to be reversed by subtracting the original physical scale score from 100.

For example, if the Physical Scale score is 80 and the other three scale scores are 30, 25, and 25 respectively, the corrected Physical Scale score is 100-80=20.

#### Step 4: Compute the Summary Score of Productivity Loss

After the 4 WLQ scale scores are determined, then the WLQ Productivity Loss Score is computed. The WLQ Productivity Loss Score indicates the percentage decrement in work output due to health problems. This is important when comparing WLQ results to other published scales, which sometimes measure productivity using the metric of time (productivity hours lost) or effort (percent effectiveness). The WLQ Productivity Loss Score tells you the estimated percent difference in an employee's at-work productivity compared to employees who do not have health-related work limitations (a healthy benchmark group).

To obtain the WLQ Productivity Loss Score, the following 2 steps are performed:

(i) Calculate the WLQ Index

#### (ii) Convert the WLQ Index into the WLQ Productivity Loss Score

#### Calculate the WLQ Index

The WLQ Productivity Loss score is based on a weighted sum of the scores from the 4 WLQ scales (Time Management, Physical, Mental-Interpersonal, and Output). The resulting score (known as the WLQ Index) is in the form of the natural log of work productivity. If a scale score is missing (in other words, it could not be computed using the procedures described previously), then Step 4 cannot be completed.

If there are scores for each of the WLQ's four scales, the following formula is used:

WLQ Index =  $(\beta 1*WLQ \text{ Time Scale} + \beta 2*WLQ \text{ Physical Scale} + \beta 3*WLQ \text{ Mental-Interpersonal Scale} + \beta 4*WLQ \text{ Output Scale}),$  $where <math>\beta 1 = 0.00048$ ,  $\beta 2 = 0.00036$ ,  $\beta 3 = 0.00096$ , and  $\beta 4 = 0.00106$ 

Convert the WLQ Index into the WLQ Summary Productivity Loss Score

The final step needed to generate the WLQ Productivity Loss Score is to convert the WLQ Index score to a percentage. The formula is as follows:

WLQ Productivity Loss Score =  $(1 - \exp(-WLQ \text{ Index}))$ 

('exp' stands for exponent. Therefore, to obtain the Productivity Loss Score, take the exponent of the negative WLQ Index score and subtract the result from 1.)

This result is then multiplied by 100 to express the score as a % of at-work productivity loss.

For example, if the four WLQ scale scores for the Time Management, Physical, Mental-Interpersonal, and Output scales were 25, 35, 25, and 40, respectively, the WLQ Index score would be calculated as:

(0.00048\*25) + (0.00036\*35) + (0.00096\*25) + (0.00106\*40) = 0.091.

Then the Productivity Loss score would be calculated as:  $1-\exp(-0.091)=0.08698$ . This is then multiplied by 100 (i.e., 0.08698\*100 = 8.698%) to get the % of at-work productivity loss.

The resulting WLQ Productivity Loss score is a relative measure. It is interpreted as the percentage of productivity loss in the past two weeks due to presenteeism relative to a healthy benchmark sample. The benchmark sample consists of employees who had WLQ scale scores of zero (not limited by health). It is not necessary to further adjust scores by age, gender, or other demographic characteristics. The maximum attainable for WLQ index (with all scales at 100) is 28.6% and the maximum attainable productivity loss is 24.9%.

#### 5.3.14.2. Analysis Methods

Descriptive statistics of actual values on Baseline, Day 8, Day 22, and Day 42 and changes from baseline to Day 8, 22, and 42 will be provided by treatment group for each of the 8 items, the 4 WLQ scales, and the WLQ Productivity Loss score.

Each of the 8 items will also be summarized at each visit with frequency counts and percentage of subjects by treatment group.

#### 5.3.15. MADRS-6

#### 5.3.15.1. Definition

MADRS-6 is the depression subscale of the full MADRS, including the following 6 items: Apparent Sadness, Reported Sadness, Inner tension, Lassitude, Inability to feel, Pessimistic thoughts.

A total score (0 to 36) is calculated by adding the scores of all 6 items. Higher scores represent a more severe condition. Imputation of the total score will be performed only when 1 item score is missing. If 2 or more items are missing, the total score will be left missing. The total score will be imputed by calculating the sum of the scores of the non-missing items and multiplying it by the ratio of the maximum possible number of items (i.e., 6) to the number of non-missing items (i.e., 5).

The MADRS-6 change from baseline at Week 6 is calculated as (MADRS-6 total score at Week 6 – Baseline MADRS-6 total score). Negative changes in MADRS-6 total score indicate improvement.

## 5.3.15.2. Analysis Methods

Descriptive statistics of the actual values on Baseline, Day 8, Day 22, and Day 42 and the change from baseline to Day 8, 22, and 42 will be presented for MADRS-6 total score by treatment group.

The change from baseline to Day 8, 22, and 42 in MADRS-6 total score will be analyzed using the same MMRM as described in Section 5.2.3.1 for the primary efficacy endpoint, with the continuous covariate "baseline MADRS total score" changed to "baseline MADRS-6 total score".

As a sensitivity analysis, the change in MADRS-6 total score from baseline to the end of Week 6 will be analyzed using an ANCOVA model, using LOCF data. The derivation of the LOCF values is described in Section 5.2.3.3. The ANCOVA model will include factors for treatment, region, baseline insomnia status (present/absent), and baseline MADRS-6 total score as a continuous covariate. A 90% CI for the difference in LS Means and p-value will be calculated based on the contrast test statistic for each JNJ-42847922 dose level.

## 6. SAFETY

All safety analyses will be based on the safety analysis set.

#### 6.1. Adverse Events

The verbatim terms used in the CRF by investigators to identify AEs will be coded using the Medical Dictionary for Regulatory Activities (MedDRA). Any AE occurring at or after the initial administration of study drug through the day of last dose plus 2 days is considered to be treatment-emergent. If the AE occurs on the day of the initial administration of study drug, and either the AE time or time of administration are missing, then the AE will be assumed to be treatment-emergent. If the AE date is recorded as partial or completely missing, then the AE will be considered to be treatment-emergent unless it is known to be prior to the first administration of study drug based on partial onset date or resolution date.

All reported treatment-emergent adverse events (TEAEs) will be included in the analysis. For each TEAE, the number and percentage of subjects who experience at least 1 occurrence of the given event will be summarized by system organ class, preferred term, and treatment group.

Summary tables will be provided for:

- TEAEs
- TEAEs occurring in  $\geq$ 5% of subjects in any treatment group
- Treatment-emergent serious AEs (SAEs)
- TEAEs leading to discontinuation of study drug
- TEAEs by severity
- TEAEs by relationship to study drug

For the summaries of TEAEs by severity/relationship to study drug, the observation with the most severe occurrence/closest relationship to study drug will be chosen if there is more than one incident of the same TEAE for the subject.

In addition, a summary table will be generated showing the number and percentage of subjects who experience at least 1 occurrence of a given TEAE by system organ class, preferred term, lowest level term, and treatment group.

A summary of all somnolence-related TEAEs (MedDRA preferred terms: somnolence, hypersomnia, and sedation; regardless of start time) will be presented.

Adverse events of special interest are cataplexy, sleep paralysis, and complex, sleep-related behaviors (parasomnias). Subjects with TEAEs of special interest will be presented separately, by preferred term and treatment group. The AEs to be included in the summary of TEAEs of special interest are marked as such on the AE CRF.

A summary table of non-TEAEs occurring on or after the date of last dose of study drug plus 3 days until the overall reference end date for the study will also be provided.

In addition to the summary tables, listings will be provided for subjects who:

- Died
- Had SAEs

- Had AEs leading to discontinuation of study drug
- Had somnolence-related TEAEs
- Had TEAEs of special interest

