#### **Double-blind Phase**

The analysis reference start date of the double-blind analysis phase is the date of the first dose of double-blind medication. The analysis reference end date of the double-blind analysis phase (except for Adverse Events) is the maximum of the date of the last visit in the double-blind phase and date of completion or early withdrawal from the double-blind phase (Trial Disposition for Double-blind Phase CRF page). For Adverse Events, the analysis reference end date of the double-blind analysis phase is the date of the last dose of study drug plus 2 days. For randomized subjects who did not receive any medication in the double-blind phase, both analysis reference start and end dates are missing for the double-blind analysis phase.

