#### 2.9. Imputation Rules for Missing Adverse Event (AE) Dates

Partial AE onset dates will be imputed as follows:

- If the onset date of an AE is missing day only, it will be set to:
  - First day of the month that the AE occurred, if month/year of the onset of AE is different than the month/year of the study drug start
  - The day of study drug start, if the month/year of the onset of AE is the same as month/year of the study drug start date and month/year of the AE resolution date is different
  - The day of study drug start or day of AE resolution date, whichever is earlier, if month/year of the onset of AE and month/year of the study drug start date and month/year of the AE resolution date are the same.
- If the onset date of an AE is missing both day and month, it will be set to the earliest of:
  - December 31 of the year of onset, if the year of onset is prior to the year of the study drug start date
  - $\circ~$  January 1 of the year of onset, as long as this date is on or after the study drug start date
  - Month and day of the study drug start date, if this date has the same year as the year that the AE occurred
  - The AE resolution date.
- Completely missing onset dates will not be imputed.

Partial AE resolution dates will be imputed as follows:

- If the resolution date of an AE is missing day only, it will be set to the earlier of the last day of the month of occurrence of resolution or the day of the date of death, if the death occurred in that month.
- If the resolution date of an AE is missing both day and month, it will be set to the earlier of December 31 of the year or the day and month of the date of death, if the death occurred in that year.
- Completely missing resolution dates will not be imputed.

AE onset/resolution dates with missing times will be imputed as follows:

- A missing time of onset of an AE will be set to the earlier of:
  - o 00:01 as long as the onset date is different from the study drug start date
  - The time of the study drug start if this is the same day the AE occurred.
- The missing time of resolution of an AE will be set to 23:59.

If a missing time is associated with a partial date, the date will be imputed first prior to imputing the time.

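### SAP 6.1 counts a partially dated adverse event as treatment-emergent even when its recorded month or year already shows onset after the last dose plus 2 days

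*SAP*

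**What the plan says.** SAP Section 6.1 opens with a two-sided window: any event from the first administration "through the day of last dose plus 2 days is considered to be treatment-emergent". The Double-blind Phase definition in SAP Section 2.2 agrees, counting in days: "For Adverse Events, the analysis reference end date of the double-blind analysis phase is the date of the last dose of study drug plus 2".

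Later in the same paragraph of 6.1 comes the rule for incomplete dates, whether partial or wholly absent: "the AE will be considered to be treatment-emergent unless it is known to be prior to the first administration of study drug". The evidence for that single exception may be a partial onset date or the date of resolution. No exception covers an onset known to fall after the window.

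Section 6.1 also plans a table for events after the window: "A summary table of non-TEAEs occurring on or after the date of last dose of study drug plus 3 days", running to the overall reference end date of the study.

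SAP Section 2.9 separately imputes incomplete onset dates. With only the day missing, the imputed date is "First day of the month that the AE occurred, if month/year of the onset of AE is different" from that of the first dose. Completely missing onset dates are not imputed. Neither section says whether the imputed date or the 6.1 sentence decides treatment-emergent status.

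**The concern.** The partial-date rule drops the upper limit of the window it serves. If an onset is recorded only as a month that begins after the last dose plus 2 days, the record itself shows that the event is post-treatment. Section 6.1 nonetheless makes it a TEAE, because it is not known to precede the first dose.

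Such an event would then enter the TEAE tables and, where relevant, those for treatment-emergent serious events, somnolence and events of special interest. It would be missing from the post-treatment table. The distinction matters somewhat here because the study also looks for withdrawal effects after dosing stops. Since the SAP does not rank 2.9 against 6.1, two programmers following it in good faith could also produce different tables.

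**Working it through.** The documents give no figure on this point, so there is none to reproduce. The check has three parts.

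**1. Can a post-window onset be recorded?** Inputs: last planned dose on Day 41 (Protocol Section 6); window closing 2 days later (SAP 6.1); adverse events collected until the follow-up visit (Protocol Section 9.6), scheduled for Days 49-56 (Time and Events Schedule).

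- Window closes on Day 41 + 2 = Day 43.
- Post-window collection runs from Day 44 to Day 49 at the shortest (6 days) and to Day 56 at the longest (13 days).

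So it can.

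**2. A worked case.** First dose 15 June 2018 (illustrative), so Day 41 is 25 July, the window closes on 27 July, and Days 49-56 are 2-9 August. The day of onset is missing.

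| Onset recorded as | 6.1 as written | 2.9 imputed date, then the window | 6.1 with an upper-bound exception |
|---|---|---|---|
| May 2018 | not a TEAE | 1 May: not a TEAE | not a TEAE |
| June 2018 | TEAE | 15 June: TEAE | TEAE |
| July 2018 | TEAE | 1 July: TEAE | TEAE |
| August 2018 | **TEAE** | 1 August: **not a TEAE** | not a TEAE |

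The readings differ only for August. This is general: if the recorded month is later than the month containing the last dose plus 2 days, the first of that month must lie after the window. In every such case 6.1 as written and the 2.9 date disagree. An event recorded as July stays treatment-emergent under all three, although its true onset could have been 28-31 July, because the month alone does not settle it.

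**3. How often does the month alone show it?** Assume all 41 doses are taken, start dates are spread evenly over the calendar, and onset is equally likely on each post-window day. The average month is 1461/48 = 30.44 days. An onset k days after the window closes falls in a later month with probability about k/30.44. Averaging over k = 1 to n gives ((n + 1)/2)/30.44.

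- Follow-up to Day 49, n = 6: 3.5/30.44 = 11.5%, about 12%.
- Follow-up to Day 56, n = 13: 7/30.44 = 23.0%, about 23%.

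The share of subjects with at least one such day is n/30.44: 6/30.44 = 20% and 13/30.44 = 43%. Enumerating every start date over four calendar years gives the same values (11.5% and 23.0% of onset days; 19.7% and 42.7% of subjects).

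These percentages apply only to events that have a partial onset date and a post-window onset. The documents do not give the number of those.

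**The case against.** The best defence is that 6.1 is deliberately conservative: when a date is incomplete, count the event against treatment. For a date that is truly unknown this is a usual convention and should stay. It does not cover a date whose recorded part already settles the matter. The SAP shows as much in Section 2.10.2, where a medication with a partial start date counts as concomitant in the double-blind phase only if its start month and year are no later than those of the phase end. That is the upper bound that 6.1 lacks.

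It can also be said that 2.9 assigns dates while 6.1 assigns status, so the two do not strictly contradict each other, and that a programmer who classifies on the imputed date avoids the problem. Both points are fair. They leave the 6.1 sentence in conflict with its own window and the order of precedence unstated.

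The defence is strongest on consequence. The adverse event outputs are counts and percentages with no planned test, the rule is the same in every arm, and serious events are also listed by subject. An event reported at a visit within days of onset is unlikely to lack its day. All of this stands, and it keeps the point minor.

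Three stronger readings are tempting, and the documents do not support them:

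- A reader might infer that the same event is counted in both tables. The second table is restricted to non-TEAEs, so an event that 6.1 makes a TEAE cannot enter it.
- A reader might suppose that partial dates would come mainly from early discontinuers reporting by recall. Nothing in the documents says so, and those subjects also have end-of-treatment and follow-up assessments (Protocol Sections 9.1.4 and 10.2).
- A reader might extend the post-window period to 30 days after the last dose, which would raise the share. That period concerns serious events only (Protocol Section 12.3.1). They require a physician-signed form within 24 hours (Section 12.3.2), so they seem among the records least likely to keep a partial date.

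**Conclusion.** The partial-date rule in SAP 6.1 is wrong as written, not merely short of detail: followed literally, it classes as treatment-emergent an event whose recorded month or year shows that it is not. The importance is minor. Three conditions must coincide: a partial onset date, an onset after the last dose plus 2 days, and a change of month. Under the even-calendar and full-dosing assumptions, the last condition holds for about 12% to 23% of post-window onset days. The number of partial dates is not given and is probably very small. Any error adds to the TEAE counts and removes from the post-treatment table. No efficacy, sample-size or dose-response result depends on it.

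**What to change.** In SAP Section 6.1, extend the exception so that a partially dated event is treatment-emergent unless it is known to precede the first dose, *or known, from the partial onset date, to be after the date of last dose of study drug plus 2 days*. Keep completely unknown onset dates as treatment-emergent, with the existing exception for events known to precede the first dose. Add one sentence stating whether the Section 2.9 imputed date is used to classify events as treatment-emergent.

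The cost is one clause and one sentence in the SAP, with the matching change in programming. No new data are needed.

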As with any CNS-active medication, investigators should monitor carefully and document any CNS-related adverse event including tremor, ataxia, abnormal sensation, confusion, or possibility of seizure.

Adverse Events of Special Interest

The following adverse events are considered to be of special interest in this study:

- Cataplexy (sudden, transient episode of muscle weakness accompanied by conscious awareness)
- Sleep paralysis (the experience of not being able to move, react, or speak when falling asleep/awakening)
- Complex, sleep-related behaviors/parasomnias such as confusional arousals, somnambulism (sleep walking), sleep terrors, bruxism (teeth grinding), sleep sex, sleep-related eating disorder, sleep behavior disorder, and catathrenia (REM-associated end-inspiratory apnea/breath holding).

Investigators are instructed to inquire about the occurrence of such events during the collection of adverse events at each visit. When reported, the investigator will be required to complete a detailed summary of the event and its clinical course utilizing the AE of special interest narrative form as soon as information on the outcome (recovered, resolving, or ongoing) is available. In addition, the AE should be marked as an AE of special interest in the CRF. Note: If the event

meets the seriousness criteria (see Section 12.1.1), the Serious Adverse Events Form must also be completed according to the serious adverse events reporting timeline described in Section 12.3.2, ie, within 24 hours of having become aware of the event, even if all details are not available.

Clinical Laboratory Tests

Blood samples for serum chemistry and hematology and a random urine sample for urinalysis will be collected. The investigator must review the laboratory results, document this review, and record any clinically relevant changes occurring during the study in the Adverse Event section of the CRF. The laboratory reports must be filed with the source documents. Clinical laboratory assessments (including TSH, hematology, serum chemistry, HbA1c, lipid panel, and urinalysis) should be performed under fasting conditions.

The following tests will be performed during the study:

- Hematology Panel
 - -hemoglobin -platelet count
 - -hematocrit -percent reticulocytes
 - -red blood cell (RBC) count
 - -white blood cell (WBC) count with differential

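### SAP 6.1 selects adverse events of special interest by the CRF mark alone, so a reported but unmarked event would be missing from the special-interest summary and listing

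*SAP*

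**What the plan says.** SAP 6.1 defines the category by clinical concept: "Adverse events of special interest are cataplexy, sleep paralysis, and complex, sleep-related behaviors (parasomnias"). It commits to a separate display: "Subjects with TEAEs of special interest will be presented separately, by preferred term and treatment group". It then states how events enter that display: "The AEs to be included in the summary of TEAEs of special interest are marked as such on the AE CRF". The same section promises a subject listing for TEAEs of special interest and gives no other selection rule for it.

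The mark comes from the site. Protocol 9.6 (Safety Evaluations, Adverse Events of Special Interest) names the events, with an open-ended set of examples for the parasomnias. It tells investigators to ask about them ("Investigators are instructed to inquire about the occurrence of such events during the collection of adverse events at each visit") and to complete a narrative form, and then adds: "In addition, the AE should be marked as an AE of special interest in the CRF".

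For somnolence, SAP 6.1 uses a different method, selection by coded term: "A summary of all somnolence-related TEAEs (MedDRA preferred terms: somnolence, hypersomnia, and sedation; regardless of start time) will be presented".

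**The concern.** Protocol 9.6 and 11.7 define these events by what happened to the subject. Being marked is not part of that definition. SAP 6.1 turns a data-entry step at the site into the criterion for inclusion, although every adverse event is already MedDRA-coded and the same section selects somnolence by preferred term. Neither document describes a search of coded terms for special-interest events, or a comparison of such a search with the mark.

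An event coded as sleep paralysis but left unmarked would fit the definition and still be outside the special-interest summary. By the same rule it would be outside the special-interest listing. Marks could be missed or applied unevenly because the parasomnia category is open-ended and no term list guides borderline cases. Nightmare, for example, was reported in an earlier MDD study (Protocol 1.1.2), and the documents do not say whether it counts.

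Safety and tolerability form a primary objective (SAP 1.1), and the results are to inform dose selection for Phase 3 (Protocol 1.2). A reader will go to the special-interest table first for these events, so it should be complete.

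**Working it through.** The documents give no figure on this point, so there is none to reproduce. The check has two parts: tracing an unmarked event through the planned outputs, and a calculation for scale.

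**Where a reported but unmarked, non-serious sleep paralysis event would appear under SAP 6.1**

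- All-TEAE table by system organ class, preferred term and treatment group: yes. The SAP says "All reported treatment-emergent adverse events (TEAEs) will be included in the analysis", and no frequency threshold applies to this table.
- Table that adds lowest level term: yes.
- Severity and relationship tables: yes.
- Table of TEAEs in at least 5% of subjects in any group: unlikely for a rare term. With 280 × 1/4 = 70 subjects in an active arm (2:1:1 assumed unchanged), 5% is 3.5, so 4 subjects would be needed.
- Special-interest summary: no, because the mark is absent.
- Special-interest listing: no, by the same definition.
- Other SAP 6.1 listings (deaths, serious events, discontinuations due to adverse events, somnolence-related events): no, unless the subject also meets one of those criteria.

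The event is therefore kept in the general tables and lost only from the two special-interest outputs.

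**Scale, for illustration only**

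Inputs:
- Prior sleep paralysis cases: 3 (Protocol 3.2, Adverse Events of Special Interest).
- Prior subjects given at least one dose: 271 (Protocol 1.1.2).
- Planned sample size: about 280 (SAP 1.2).
- Active subjects, assuming 2:1:1 throughout: n = 280 × (1 + 1)/(2 + 1 + 1) = 140.
- Share of events marked, s: not given in the documents, so a range is assumed.

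Prior rate: p = 3/271 = 0.0111, or 1.1%.

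Expected events in the table: n × p × s. Chance that the table shows at least one: 1 − (1 − p × s)^n.

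| s (assumed) | Expected events shown | Chance of at least one |
|---|---|---|
| 1.0 | 140 × 0.01107 = 1.55 | 79% |
| 0.9 | 1.39 | 75% |
| 0.8 | 1.24 | 71% |
| 0.5 | 0.77 | 54% |

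With complete marking, one or two cases would be expected. If there is one case and its mark is missed, the sleep paralysis row is empty. If there are two and one is missed, the row is halved.

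The prior rate pools single and multiple dosing, healthy subjects and patients, and several doses. One of the 3 cases was at 80 mg, twice the top dose here. The calculation shows only that counts would be small. It says nothing about how often marks are missed.

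**The case against.** The strongest objection concerns consequence. An unmarked event does not leave the report: it is counted by treatment group in the all-TEAE tables by preferred term and again by lowest level term. A reader might infer that a missed mark removes half or all of the signal. The documents do not support that, since only the special-interest summary and listing are affected. Neither document gives the special-interest summary a privileged status. Protocol 11.7 says only that these subjects may be shown separately, so the SAP already commits to more.

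A reader might also infer a gap for subjects enrolled before Amendment 5, because the amendment log shows that the sentence on marking was added then. The log does not bear this out. Before that amendment, investigators already had to give a detailed summary of each such event on a CRF page. Nothing shows that earlier events lacked a special-interest record or were left unmarked.

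There are also surrounding safeguards: active inquiry at each visit, the narrative form, sponsor queries (Protocol 17.5), CRF review (17.6) and source comparison on site (17.8). A completed narrative without a mark could expose the mismatch. All of this stands, but none of it is a stated reconciliation of coded terms with the mark.

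Finally, a term list is not better in every respect. Cataplexy recorded as transient weakness may be recognised by an investigator and missed by a list. That is a sound reason to keep the mark, and it supports using both methods rather than replacing one with the other.

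**Conclusion.** The point holds as a limited one. SAP 6.1 makes the CRF mark the only stated route into the special-interest outputs, so a reported but unmarked event would be missing from that summary and listing while remaining in the all-TEAE tables. This is a risk of undercount in descriptive outputs. It affects no test, estimate or decision rule, and the documents do not show that it has occurred.

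The number of missed marks cannot be estimated from the documents. The case for acting rests on small expected counts: about 1.5 sleep paralysis cases if the pooled rate of 3/271 applied to about 140 active subjects. That figure assumes an unchanged 2:1:1 ratio, which the interim analysis may alter, and it covers sleep paralysis only. At such counts one missed mark could visibly change the table. The change is worth making as a cheap improvement.

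**What to change.** In SAP 6.1, define TEAEs of special interest as the union of (a) events marked on the AE CRF and (b) events whose MedDRA preferred term is on a prespecified list for cataplexy, sleep paralysis and the parasomnias named in Protocol 9.6. Fix the list before unblinding and use the same definition for the summary and the listing. While still blinded, review and list every mismatch in both directions: listed term without a mark, and mark without a listed term.

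The union cannot drop an event that is now included, and it keeps the investigator's recognition of events that are coded unhelpfully. The cost is a short term list and one blinded medical review. The downside is that a few marginal terms may enter the table, and the mismatch listing would make these visible.
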